### **Time Point Assessments**

The frequency and schedule of tumor assessments is defined in the protocol. The schedule is to be maintained regardless of whether study treatment is given, reduced, held, or discontinued, including for subjects randomized to placebo who cross over to receive cabozantinib (Appendix B).

At baseline, tumors and lymph nodes are classified and documented as target or nontarget lesions per the definitions provided above. It is possible to record multiple nontarget lesions involving the same organ as a single item (eg, ‘multiple liver metastases’). At all postbaseline (follow-up) evaluations the baseline classification (target, nontarget) is to be maintained and lesions are to be documented and described in a consistent fashion over time (eg, recorded in the same order on source documents).

At each assessment, a sum of the diameters (longest for nonnodal lesions, short axis for nodal lesions) for all target lesions will be calculated and included in source documents. The *baseline sum of the diameters* (SoD) will be used as reference to further characterize any objective tumor regression in the measurable dimension of the disease. The lowest SoD (nadir) since (and including) the baseline value will be used as reference for evaluating progression.

After baseline, target lesions should have the actual size documented, if possible, even if the lesions become very small. If in the opinion of the radiologist the lesion has likely disappeared, 0 mm should be recorded. If the lesion is present but too small to measure, an indicator for ‘too small to measure’ should be included in source documents.

Nontarget lesions are to be assessed qualitatively (present, resolved, or unequivocal progression) and new lesions, if any, are to be documented separately.

At each evaluation, progression status is to be determined based upon the time point status for target lesions, nontarget lesions, and new lesions.

Finding of new lesions should not be attributable to differences in scanning technique, change in imaging modality or findings thought to represent something other than tumor. Necrosis of pre-existing lesions as part of a response to treatment should be excluded before defining a ‘new’ cystic lesion. A lesion identified on a follow-up study in an anatomical location that was not scanned at baseline is considered a new lesion. If a new lesion is equivocal because of its small size, repeat scans need to confirm there is definitely a new lesion, and progression should be declared using the date of the initial scan.

## RESPONSE CRITERIA

---

### Target Lesion Time Point Response (TPR)

---

|                                 |  |
|---------------------------------|--|
| Complete Response (CR)   | 

Disappearance of all target lesions. All pathological lymph nodes (whether target or non-target) must have reduction in short axis to < 10 mm.

  |
| Partial Response (PR)    | 

At least a 30% decrease in SoD of target lesions, taking as a reference the baseline SoD

   |
| Stable Disease (SD)      | 

Neither sufficient shrinkage to qualify for PR nor sufficient increase to qualify for PD.

  |
| Progressive Disease (PD) | 

At least a 20% increase in the SoD of target lesions, taking as a reference the smallest (nadir) SoD since (and including) baseline. In addition to the relative increase of 20%, the SoD must also demonstrate an absolute increase of at least 5 mm.

 |
| Not Applicable (NA)      | 

No target lesion identified at baseline.

   |
| Unable to Evaluate (UE)  | 

One or more target lesions are not imaged and the remainder of the SoD compared with the nadir SoD does not meet the criterion for PD.

   |

---

SoD, baseline sum of diameters (longest for non-nodal lesions; short axis for nodal lesions)

If the target lesion for a subject meet the criteria for both PR and PD at a given time point, the target lesion response is PD.

If the nadir of SoD is 0 (ie, the subject had a prior target lesion CR), the reappearance of any prior target lesion to any degree constitutes PD.

---

### Non-Target Lesion Time Point Response (TPR)

---

|                                 |   |
|---------------------------------|---|
| Complete Response (CR)   | 

Disappearance of all non-target lesions. All lymph nodes must be non-pathological in size (< 10 mm short axis)

   |
| Non-CR / Non-PD          | 

Persistence of one or more non-target lesion(s).

  |
| Progressive Disease (PD) | 

Unequivocal progression of non-target lesions. Unequivocal progression should normally trump target lesion status. It must be representative of overall disease status change, not a single lesion increase

 |
| Not Applicable (NA)      | 

No non-target lesions identified at screening

   |
| Unable to Evaluate (UE)  | 

One or more non-target lesions are not imaged and the remaining non-target lesions do not meet the criterion for PD.

  |

---

---

**New Lesion Time Point Response (TPR)**

---

|            |  |
|------------|--|
| Yes | 

Lesion present at follow-up visit either for the very first time or re-appearing (ie, lesion was present at baseline, disappeared at a follow-up visit and re-appeared later). Confirmation of bone scan findings must be obtained by performing CT or MRI of the area of concern. Preferred method for confirmation is MRI.

 |
| No  | 

No new lesions present at follow-up.

   |

---

CT, computed tomography; MRI, magnetic resonance imaging.

---

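### Appendix H scores a baseline lesion that vanishes and re-appears as a new lesion, hence PD, although its own sum-of-diameters rule can still give PR; this mainly affects BIRC PFS and duration of response

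*Combined protocol and SAP*

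**What the plan says.** All of the following except the last item is in protocol Appendix H.

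- **New Lesion Time Point Response:** the answer is Yes for a lesion seen for the first time, and also for one that is "re-appearing (ie, lesion was present at baseline, disappeared at a follow-up visit and re-appeared later". Target and non-target lesions are not distinguished.
- **Evaluation of Overall Time Point Response:** a Yes for new lesion gives PD whatever the target and non-target status. That entry carries a double asterisk whose note is not in the text available.
- **Time Point Assessments:** "At all postbaseline (follow-up) evaluations the baseline classification (target, nontarget) is to be maintained". A target lesion judged likely to have gone is entered as 0 mm; one still visible but too small to measure is flagged separately. A new lesion that is equivocal because it is small needs repeat scans, with progression dated back to the first scan if it is confirmed.
- **Target Lesion Time Point Response, PD:** "At least a 20% increase in the SoD of target lesions, taking as a reference the smallest (nadir) SoD since (and including) baseline", and in addition "the SoD must also demonstrate an absolute increase of at least 5 mm". A separate sentence deals with re-appearance: "If the nadir of SoD is 0 (ie, the subject had a prior target lesion CR"), then "the reappearance of any prior target lesion to any degree constitutes PD".
- **Non-Target Lesion Time Point Response, PD:** progression must be unequivocal, and "It must be representative of overall disease status change, not a single lesion increase".
- **SAP:** best overall response is taken only through the first overall PD, and CR or PR needs confirmation at least 28 days later (8.1.1.1). PFS runs to radiographic PD per BIRC or death (8.1.2.4). Duration of response uses the same progression dates (8.4.2).

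**The concern.** The appendix handles re-appearance in two ways that do not agree. The target-lesion section treats it as PD in itself only after every target lesion has gone; in all other cases the lesion is measured, returns to the SoD and must pass the 20% and 5 mm tests. The new-lesion table has no such condition. If that table governs, the condition on nadir 0 does no work, and the 20% and 5 mm tests are bypassed for any target lesion once recorded as 0 mm.

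A lesion has to disappear before it can re-appear, and disappearance is mainly a feature of responders. With planned response rates of 35% and 2%, the extra PDs would fall mostly on cabozantinib. They would bring PFS events forward, shorten duration of response and pull the hazard ratio toward 1. The investigator-read sensitivity analysis (PFS-EP-3) uses the same criteria and would not separate the effect out.

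**Working it through.** **1. One scan under both rules.** Assumed target lesions, in mm:

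| Visit | Lesions | SoD | Change from baseline |
|---|---|---|---|
| Baseline | 40 + 20 + 10 | 70 | – |
| Week 8 | 28 + 12 + 0 | 40 | −30/70 = −43% (PR) |
| Week 16 | 28 + 12 + 4 | 44 | −26/70 = −37% |

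SoD rule at Week 16: the change from nadir is 4/40 = +10% and +4 mm. Both are below the PD limits, so the result is PR, and the Week 8 response is confirmed. New-lesion rule: Yes, so overall PD. There is then no confirmed response, and there is a PFS event at 16 × 7 / 30.4375 = 3.7 months.

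**2. How large a re-appearing lesion can be without meeting the SoD rule.** With the other lesions unchanged and a non-zero nadir N, PD needs a lesion of at least max(5 mm, 0.2N). For N = 40 that is 8 mm. Once N exceeds 50 mm it is more than 0.2 × 50 = 10 mm, the CT measurability limit. The conflict is therefore not confined to tiny, doubtful lesions.

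**3. Where the rules agree.** At nadir SoD 0 both give PD. They conflict for a target lesion re-appearing over a non-zero nadir. They conflict less directly for a single non-target lesion that re-appears without unequivocal progression.

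**4. The plan's own power figures** (not disputed).
- ORR, 67 vs 33 subjects, 35% vs 2%, two-sided 0.01, pooled variance. The pooled rate is (67 × 0.35 + 33 × 0.02)/100 = 0.241. Power = Φ[(0.33 − 2.576 × 0.0910)/0.0632] = 93.5%, against the stated figure of more than 90%. Exact Fisher power is 97.0%.
- PFS, 193 events, HR 0.61, two-sided 0.04, 2:1. Power = Φ[√(193 × 2/9) × |ln 0.61| − 2.054] = 88.2% by the Schoenfeld formula. Simulation under the plan's assumptions gives 0.89–0.91, against the stated 90%.

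**5. PFS effect at assumed rates.** Simulation: 200 and 100 subjects, exponential medians 9 and 5.5 months, uniform 15-month accrual, analysis at 193 events, unstratified log-rank test at two-sided 0.04. A false PD is placed at a random 8-weekly scan from Week 16 to Week 48 if the subject is still event-free. The documents give no re-appearance rate, so two scales are shown.
- As a share of responders, 5% / 10% is 0.35 × 5% = 1.75% and 0.35 × 10% = 3.5% of the cabozantinib arm, and 0.02 × 5% = 0.1% and 0.02 × 10% = 0.2% of placebo.
- As a share of the arm, 5% / 10% of cabozantinib and 1% / 2% of placebo.

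| Assumption | False events of 193 | Cox HR shift toward 1 | Power |
|---|---|---|---|
| None | 0 | – | about 90% |
| 5% / 10% of responders | 1.7 / 3.4 | about 1% / 2–3% | about 88% / 85–86% |
| 5% / 10% of the whole arm | 5 / 10 | about 4% / 7% | 84–85% / 77–79% |

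Ranges are the spread over repeated simulation runs.

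**6. ORR effect at assumed rates.** Each lost responder costs 1/67 = 1.5 points. If 5% / 10% of cabozantinib responders lost their confirmation this way, ORR would be 0.35 × 0.95 = 33.3% or 0.35 × 0.90 = 31.5%. Pooled-variance power would be 90.6% / 86.8%, and Fisher power 95.3% / 92.8%. This is an upper limit for those rates, because it puts every re-appearance at or before the confirming scan.

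**The case against.** The strongest defence is that the overall-response table sets an order of precedence: any new lesion gives PD. A reader who follows it reaches one answer, and the nadir-0 sentence is then redundant, not contradictory. That describes how the tables combine. It does not explain why the target section attaches a condition to re-appearance that the next table removes, or how a lesion that keeps its baseline class can also be new.

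Other points limit the size and stand:

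- The repeat-scan rule for equivocal small lesions would often delay the call in a case like the 4 mm example, although a confirmed lesion is dated back to the first scan.
- Lesions flagged as too small to measure have not disappeared, so not every shrunken lesion is exposed.
- The double-asterisk note and the imaging charter are not available, and either may narrow the rule.
- The non-target wording speaks of a lesion's increase, so the conflict there is weaker.
- The bias is blinded, the same rule applies to both arms, and it works against cabozantinib. Nothing here suggests Type I error inflation.

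A reader might infer three stronger things that the documents do not support:

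- **That both primary endpoints are equally exposed.** A response already confirmed stays in best overall response (SAP 8.1.1.1), and a repeat assessment is possible from 4 weeks (protocol 5.7.6.3).
- **That the rule by itself triggers unblinding and crossover.** Both start from investigator-determined PD (protocol 3.5.2.2), and investigators are told to wait when progression is ambiguous (5.7.6.1).
- **That 5–10% of the whole cabozantinib arm is the natural scale.** That is 5/35 = 14% to 10/35 = 29% of the planned responders.

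**Conclusion.** The inconsistency is real: one scan can be PR by the SoD rule and PD overall. It bears mainly on BIRC PFS and duration of response, and on ORR only for responses not yet confirmed. The direction is toward HR = 1, with a loss of power.

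The size cannot be derived from the documents. On a responder-based assumption of 5% / 10% it is modest: about 2 or 3 false events among 193 and a power loss of roughly 2 to 5 points. The whole-arm figures are a pessimistic bound for the same percentages. All of this assumes that readers apply the new-lesion table as written, and that neither the missing note nor the charter overrides it.

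**What to change.** - In the New Lesion table, delete the re-appearance clause, so that a new lesion is one not present at baseline. Keep the existing provision for sites not scanned at baseline.
- State that a re-appearing target lesion is measured, added back to the SoD and judged by the target-lesion rule, with re-appearance alone being PD only at nadir SoD 0.
- State that a re-appearing non-target lesion is judged under the existing non-target rule. The documents do not support adding further conditions there.
- Reconcile this with the repeat-scan text, the overall-response table and its double-asterisk note, and the BIRC imaging charter.
- Apply one rule to all reads. Because BIRC reads are made in real time, any time point scored PD only because a baseline lesion re-appeared would need to be identified and re-read under blinded conditions.

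The cost is a few sentences in Appendix H and the charter, plus any such re-reads. No added scans are needed.

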**Evaluation of Overall Time Point Response (TPR)**

---

| Target Lesion TPR | Non-target lesion TPR | New lesion TPR | Overall TPR |
|--------------------------|------------------------------|-----------------------|--------------------|
| CR                       | CR or NA                     | No                    | CR*                |
| CR                       | Non-CR/non-PD                | No                    | PR*                |
| CR                       | UE                           | No                    | PR*                |
| PR                       | Non-PD or NA or UE           | No                    | PR*                |
| SD                       | Non-PD or NA or UE           | No                    | SD                 |
| UE                       | Non-PD                       | No                    | UE                 |
| PD                       | Any                          | No or Yes             | PD                 |
| Any                      | PD                           | No or Yes             | PD                 |
| Any                      | Any                          | Yes                   | PD**               |
| NA                       | CR                           | No                    | CR*                |
| NA                       | Non-CR/Non-PD                | No                    | Non-CR/non-PD      |
| NA                       | UE                           | No                    | UE                 |

CR, complete response; PR, partial response; SD, stable disease; PD, progressive disease, UE, unable to evaluate; NA, not applicable (no such lesions at screening);

Any = CR, PR, SD, PD, NA, or UE.

The overall response at a given time point does not depend upon the overall response assigned at any prior time point.

\* Subjects with an overall response of CR or PR must have a repeat tumor assessment performed no less than 4 weeks after the criteria for response are first met. However, the presence or absence of confirmation is not considered when assigning a time point response.

### **Confirmation**

For subjects with an overall response of PR or CR at a given time point, a repeat assessment should be performed no less than 4 weeks after the criteria for response are first met. However, the presence or absence of confirmation is not considered when assigning a time point response.

### **Best Overall Response**

Best overall response, incorporating confirmation requirements, will be derived during statistical analysis from the series of time point responses and need not be considered when assigning response at each time point.

**Appendix I: EuroQol questionnaire EQ-5D-5L, USA (English) Sample Version**  
Under each heading, please check the ONE box that best describes your health TODAY

**MOBILITY**

- I have no problems walking
- I have slight problems walking
- I have moderate problems walking
- I have severe problems walking
- I am unable to walk

**SELF-CARE**

- I have no problems washing or dressing myself
- I have slight problems washing or dressing myself
- I have moderate problems washing or dressing myself
- I have severe problems washing or dressing myself
- I am unable to wash or dress myself

**USUAL ACTIVITIES** (*e.g. work, study, housework, family or leisure activities*)

- I have no problems doing my usual activities
- I have slight problems doing my usual activities
- I have moderate problems doing my usual activities
- I have severe problems doing my usual activities
- I am unable to do my usual activities

**PAIN / DISCOMFORT**

- I have no pain or discomfort
- I have slight pain or discomfort
- I have moderate pain or discomfort
- I have severe pain or discomfort
- I have extreme pain or discomfort

[figure not shown]
**ANXIETY / DEPRESSION**

- I am not anxious or depressed
- I am slightly anxious or depressed
- I am moderately anxious or depressed
- I am severely anxious or depressed
- I am extremely anxious or depressed

- We would like to know how good or bad your health is TODAY.
- This scale is numbered from 0 to 100.
- 100 means the best health you can imagine.  
0 means the worst health you can imagine.
- Mark an X on the scale to indicate how your health is TODAY.
- Now, please write the number you marked on the scale in the box below.

YOUR HEALTH TODAY =

**The best health  
you can imagine**

**The worst health  
you can imagine**

*USA (English) © 2009 EuroQol Group. EQ-5D™ is a trade mark of the EuroQol Group*

## LIST OF ABBREVIATIONS

|         |   |
|---------|---|
| AE      | Adverse event   |
| ALP     | Alkaline phosphatase                                  |
| ALT     | Alanine aminotransferase                              |
| ANC     | Absolute neutrophil count                             |
| AST     | Aspartate aminotransferase                            |
| ATA     | Adequate tumor assessment                             |
| ATC     | Anatomical Therapeutic Chemical                       |
| BIRC    | Blinded independent radiology committee               |
| BMI     | Body mass index                                       |
| BOR     | Best overall response                                 |
| BSC     | Best supportive care                                  |
| CAPN    | Chest abdomen pelvis neck                             |
| CI      | Confidence interval                                   |
| CMH     | Cochran-Mantel-Haenszel                               |
| CR      | Complete response                                     |
| CRF     | Case report form                                      |
| CSR     | Clinical study report                                 |
| CT      | Computerized tomography                               |
| ctDNA   | Circulating DNA                                       |
| CTC     | Circulating tumor cell                                |
| CTCAE   | Common terminology criteria for adverse events        |
| CTMS    | Clinical trial management system                      |
| DBP     | Diastolic blood pressure                              |
| DSR     | Disease stabilization rate                            |
| DTC     | Differentiated Thyroid Cancer                         |
| EBRT    | External beam radiation therapy                       |
| ECG     | Electrocardiogram                                     |
| ECOG PS | Eastern Cooperative Oncology Group Performance Status |
| ECG     | Electrocardiogram                                     |
| ER      | Emergency room visit                                  |
| ETM     | Events to monitor                                     |

|        |  |
|--------|--|
| FDA    | Food and Drug Administration                 |
| FTC    | Follicular thyroid carcinoma                 |
| GFR    | Glomerular filtration rate                   |
| GGT    | Gamma-glutamyltransferase                    |
| HCRU   | Health care resource utilization             |
| HGB    | Hemoglobin                                   |
| HR     | Hazard ratio                                 |
| HRQOL  | Health Related Quality of Life               |
| ICH    | International Conference on Harmonization    |
| ICU    | Intensive care unit                          |
| IDMC   | Independent Data Monitoring Committee        |
| ITT    | Intent-To-Treat                              |
| IRT    | Interactive Response Technology              |
| LDH    | Lactate dehydrogenase                        |
| LLN    | Lower limit of normal                        |
| LLQ    | Lower limit of quantitation                  |
| MRI    | Magnetic resonance imaging                   |
| MedDRA | Medical Dictionary for Regulatory Activities |
| NE     | Not evaluable                                |
| NPACT  | Non-protocol anticancer therapy              |
| OITT   | Objective response rate intent-to-treat      |
| ORR    | Objective response rate                      |
| OS     | Overall survival                             |
| PD     | Progressive Disease                          |
| PFS    | Progression-free survival                    |
| PFS2   | Time to second disease progression or death  |
| PD-1   | Programmed cell death protein 1              |
| PD-L1  | Programmed death-ligand 1                    |
| PK     | Pharmacokinetic                              |
| PR     | Partial response                             |
| PTC    | Papillary thyroid carcinoma                  |
| qd     | Once daily                                   |

|        |  |
|--------|--|
| QOL    | Quality of Life                              |
| RAI    | Radioactive Iodine                           |
| RECIST | Response evaluation criteria in solid tumors |
| RMP    | Risk management plan                         |
| SAE    | Serious adverse event                        |
| SBP    | Systolic blood pressure                      |
| SAP    | Statistical analysis plan                    |
| SD     | Stable Disease                               |
| SmPC   | Summary of product characteristics           |
| TEAE   | Treatment emergent-adverse event             |
| TKI    | Tyrosine kinase inhibitor                    |
| TNM    | Tumor node metastasis                        |
| TSH    | Thyroid-stimulating hormone                  |
| UE     | Unable to evaluate                           |
| ULN    | Upper limit of normal                        |
| ULQ    | Upper limit of quantitation                  |
| UPCR   | Urine protein/creatinine ratio               |
| VAS    | Visual analogue scale                        |
| VEGFR  | Vascular endothelial growth factor receptor  |
| WBC    | White blood cell                             |
| WHO-DD | World Health Organization drug dictionary    |

